3.1.1 Questions Regarding Key Monitoring Behavior

Question 1:

What is your medical specialty*? Please select one from the drop-down list below.

- O General Medicine/General Practice
- O Neurology
- O Psychiatry
- O Other SPECIFY:

* NOTE – OTHER SPECIALTIES TO BE INCLUDED BASED ON AUDIENCES TO WHOM MATERIAL WAS SENT

Question 2

Please think about your patients with schizophrenia, bipolar disorder, and/or major depressive disorder who are treated with Seroquel® or Seroquel® XR. Describe the "monitoring" of metabolic factors^{*} potentially related to treatment with Seroquel® or Seroquel® XR.

A. What proportions of your patients are being monitored by you, someone else in your practice or are referred to other healthcare providers? _____%

B. What proportion of your patients is referred to other healthcare providers for monitoring?

*Monitoring of metabolic factors includes: weight at initiation and during continuing treatment, ordering or reviewing lipid panel tests, observing patients for signs or symptoms associated with hyperglycaemia, ordering or reviewing tests for blood glucose measurement for patients with diabetes mellitus or in patients with risk factors for diabetes mellitus for worsening of glycaemic control, and counseling on nutrition, exercise and maintaining a healthy lifestyle

Question 3

Thinking now of the patients that you (or someone in your practice) monitor for metabolic issues potentially related to treatment with Seroquel® or Seroquel® XR, which of the following activities do you do? Please check all that apply.

- [□] I counsel patients taking Seroquel® or Seroquel® XR on healthy eating, exercise, and healthy lifestyle improvements
- ^D I monitor patients' weight at the initiation of treatment with Seroquel® or Seroquel® XR
- ^a I monitor patients' weight on a regular basis after initiating treatment with Seroquel® or Seroquel® XR
- I monitor tests for hyperlipidemia in patients who are taking Seroquel or Seroquel® XR
- [□] I observe for signs and symptoms of hyperglycaemia in patients who are taking Seroquel® or Seroquel® XR
- I monitor patients with diabetes mellitus or with risk factors for diabetes mellitus for worsening of glucose control if they are taking Seroquel® or Seroquel® XR

Question 4

The following question has two parts; please respond to both parts of the question.

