3.2 Study Population

3.2.1 Inclusion Criteria

Health Care Professionals who were targeted to receive the metabolic educational materials and either currently prescribe or have the potential to prescribe SEROQUEL or SEROQUEL XR.

Each physician should meet all inclusion criteria and none of the exclusion criteria to be eligible for this survey. Under no circumstances can there be any exceptions to this rule.

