3.3 Sample Size

A sample size of 100 completed questionnaires from healthcare providers in each of eight selected countries representing the geographic diversity of the EU is proposed. The size of the sample was determined based on both practical and statistical considerations. There is no presumed target rate for success in risk minimization measures based upon either a process measure (e.g., receiving educational materials) nor is there a rate specified *a priori* for success in outcome measures (e.g., metabolic monitoring). A sample of 100 completed questionnaires will allow estimation of the rate for process and outcome measures with a moderate degree of precision (within 6-10 percentage points regardless of the actual level of the process or outcome measure). The table below shows the precision of the estimates for level process and outcome measure using two-sided 95% confidence intervals (CIs) obtained with the sample size of 100 completed surveys. The noted CIs are used to indicate that for any survey-estimated level of effectiveness of risk minimization, the true population level of effectiveness is at least as high as the lower limit of the 95% CI and may be as high as the upper limit of the 95% CI.

Table 1:Precision of estimated Rates of effectiveness of risk minimization
including: 1) Receiving information (as Process measure) or 2)
performance of metabolic monitoring (as Outcome measure) with a
Sample Size of 100 (Two-sided 95% Confidence Interval)

Estimated Rate	95% Confidence Interval Lower Limit	95% Confidence Interval Upper Limit
1%	0.0%	3%
6%	1.3%	10.7%
11%	4.9%	17.1%
16%	8.8%	23.2%
21%	13%	29%
26%	17.4%	34.6%

Estimated Rate	95% Confidence Interval Lower Limit	95% Confidence Interval Upper Limit
31%	21.9%	40.1%
36%	26.6%	45.4%
41%	31.4%	50.6%
46%	36.2%	55.8%
51%	41.2%	60.8%
56%	46.3%	65.7%
61%	51.4%	70.6%
66%	56.7%	75.3%
71%	62.1%	79.9%
76%	67.6%	84.4%
81%	73.3 %	88.7%

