3.4 Healthcare Provider Recruitment

A random sample of healthcare providers who were targeted to receive SEROQUEL[®] / SEROQUEL[®] XR educational materials and who are considered likely to prescribe SEROQUEL[®] / SEROQUEL[®] XR will be invited to participate. An invitation will be sent to the healthcare providers.

If the required number of completed surveys is not achieved within the expected timeframe of approximately two weeks after the first invitation, a second one will be sent to non-respondents from the original sample with subsequent follow-up to maximize participation. If these efforts do not result in the required number of surveys within three to four weeks, then a new sample of prescribers will be randomly selected.

All participating healthcare providers will be offered a nominal fee consistent with approved market value for the physician's time for a completed survey. The survey is estimated to take less than 10 minutes to complete.

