6. ANALYSIS

The survey questionnaire contains questions about the specialty of the physician sample completing the survey, questions specific to whether referrals are made to other healthcare providers for metabolic monitoring, whether the healthcare provider conducts monitoring of patients, general questions regarding receipt of the educational materials, and behavior about reading the materials. Information obtained from responses to each question of the survey will be reported as descriptive statistics. A frequency distribution of responses to each question (the number of respondents who give answers to each response option) will be presented.

Each risk minimization behavior will be evaluated individually.

Related behaviors, such as:

- Monitoring for weight
- Monitoring for signs and symptoms of hyperglycaemia and monitoring blood glucose changes in patients with diabetes mellitus will be combined to report the number of survey respondents who answered each risk minimization activity individually, any one activity and both activities. This will be expressed as a percent of the total number of respondents who answered the questions on these risk minimization activities.

Frequency distributions of the responses to having received SEROQUEL[®] / SEROQUEL[®] XR educational materials and behaviors about reading the educational materials, will also be calculated and displayed. The analysis of frequencies will include exact binomial 95% confidence intervals.

The following will be reported, as appropriate, as part of this analysis:

- The number of invitations issued to healthcare providers
- The number of healthcare providers screened for participation
- The number of healthcare providers eligible for participation
- The number of healthcare providers who completed the survey

- Description of healthcare provider survey participants, including:
 - Specialty of respondent
 - Country of practice
- Frequency distribution of responses to each survey question (the number of respondents who give each answer to each question)
- Percent of respondents selecting desired response to each question relating to each risk minimization activity and 95% confidence interval
- Percent of respondents demonstrating success of composite risk minimization activities and 95% confidence interval

Additional analyses may be performed as needed.

Risk Minimization Physician Survey Protocol

Drug Substance	Quetiapine fumarate
Study Code	D1443C000127
Edition Number	1

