Appendix B Questionnaire

QUESTIONNAIRE

The questionnaire is designed to be administered as an on-line survey via Internet. The following are mock-up version of what the successive screens that would be displayed

Screen 3 Question 1:

What is your medical specialty*? Please select one from the drop-down list below.

- O General Medicine/General Practice
- O Neurology
- O Psychiatry
- O Other SPECIFY:

* NOTE – OTHER SPECIALTIES TO BE INCLUDED BASED ON AUDIENCES TO WHOM MATERIAL WAS SENT

Screen 4 Question 2:

Instructions: Please think about your patients with schizophrenia, bipolar disorder, and/or major depressive disorder who are treated with Seroquel® or Seroquel® XR. Describe the "monitoring" of metabolic factors^{*} potentially related to treatment with Seroquel® or Seroquel® XR.

- What proportions of your patients are being monitored by you, someone else in A. your practice or are referred to other healthcare providers? %
- What proportion of your patients is referred to other healthcare providers for B. monitoring? %

*Monitoring of metabolic factors includes: weight at initiation and during continuing treatment, ordering or reviewing lipid panel tests, observing patients for signs or symptoms associated with hyperglycaemia, ordering or reviewing tests for blood glucose measurement for patients with diabetes mellitus or in patients with risk factors for diabetes mellitus for worsening of glycaemic control, and counseling on nutrition, exercise and maintaining a healthy lifestyle

Screen 5 Question 3:

Instructions: Thinking now of the patients that you yourself monitor for metabolic issues potentially related to treatment with Seroquel® or Seroquel® XR, which of the following activities do you perform? Please check all that apply.

GEL Version ID: CNS.000-362-594.2.0 Approved Date Printed: 04-Jan-2013 Approved by [name] 21 Dec 2012 15:02:47

- ^a I counsel patients taking Seroquel® or Seroquel® XR on healthy eating, exercise, and healthy lifestyle improvements
- I monitor patients' weight at the initiation of treatment with Seroquel® or Seroquel® XR
 I monitor patients' weight on a regular basis after initiating treatment with Seroquel® or
- Seroquel® XR
- [□] I monitor tests for hyperlipidemia in patients who are taking Seroquel or Seroquel® XR
- I observe for signs and symptoms of hyperglycaemia in patients who are taking Seroquel® or Seroquel® XR

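### The 6–10 point precision in Section 3.3 is not assured for outcome measures, because nothing keeps their base close to 100 per country

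*Protocol*

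**What the plan says.** Protocol Section 3.3 sets the sample: "A sample size of 100 completed questionnaires from healthcare providers in each of eight selected countries". It promises precision "within 6-10 percentage points regardless of the actual level of the process or outcome measure". Table 1 supports this "using two-sided 95% confidence intervals (CIs) obtained with the sample size of 100 completed surveys", and its title covers both receipt of information (process) and performance of metabolic monitoring (outcome).

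Four other places bear on who contributes to the outcome measures:

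- **Section 3.2.1** admits providers who "either currently prescribe or have the potential to prescribe SEROQUEL or SEROQUEL XR". Section 3.4 draws the sample from those "who are considered likely to prescribe". Neither requires a treated patient.
- **Question 2** (Section 3.1.1 and Appendix B) begins: "Please think about your patients with schizophrenia, bipolar disorder, and/or major depressive disorder who are treated with".
- **Question 3** in Appendix B begins: "Thinking now of the patients that you yourself monitor for metabolic issues potentially related to treatment with". It is a multiple-tick list with no 'none' or 'not applicable' box. Section 3.1.1 words it more broadly, to include patients monitored by someone else in the practice.
- **Section 6** says of the combined weight and glucose behaviours: "This will be expressed as a percent of the total number of respondents who answered the questions on these risk minimization activities". It also names exact binomial 95% intervals for the analysis of frequencies.

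**The concern.** One precision figure is attached to two kinds of measure whose bases may differ. Whether the materials were received can be asked of anyone who completes the survey. What a provider does for patients on the product can be reported meaningfully only by a provider who has such patients and, under the Appendix B wording, monitors them personally. A provider with only potential to prescribe counts toward the 100. So does one who refers all monitoring elsewhere, which Question 2B foresees. Either may have nothing to report under Question 3.

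The outcome indicator is one of the two components that Section 1 says the regulator described. If its base in a country is smaller than 100, the monitoring rates will be less precise than Section 3.3 says, and less precise than the receipt rate reported beside them. The precision statement claims to hold at every level of the measure, so the mid-range rates, where intervals are widest, decide whether it is true.

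**Working it through.** **Inputs.** From Section 3.3: n = 100 completed questionnaires per country, eight countries, two-sided 95% intervals, upper precision figure 10 points. From Section 6: exact binomial intervals. The share of completed questionnaires that would not contribute to the outcome measures is not given, so bases below 100 are assumptions shown as a range.

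**Step 1: reproduce Table 1.** The Wald half-width is 1.96 × √(p(1 − p)/n). For the 51% row: 1.96 × √(0.51 × 0.49/100) = 9.8 points, giving 41.2% to 60.8% as printed. All 17 rows reproduce with n = 100 (lower limit cut at 0). The table is right for its method and base, and its widest half-width is 9.8 points.

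**Step 2: vary the base at p = 50%.** The Wald half-width is 1.96 × √(0.25/n). The exact (Clopper-Pearson) limits for x events in n are the 2.5% quantile of Beta(x, n − x + 1) and the 97.5% quantile of Beta(x + 1, n − x). The half-width is taken at x = n/2, rounded down for odd n.

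| Base n | Wald (points) | Exact (points) |
|---|---|---|
| 100 | 9.80 | 10.17 |
| 96 | 10.00 | 10.38 |
| 95 | 10.05 | 10.44 |
| 90 | 10.33 | 10.73 |
| 80 | 10.96 | 11.40 |
| 70 | 11.71 | 12.20 |
| 60 | 12.65 | 13.19 |
| 50 | 13.86 | 14.47 |

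By the Wald method the 10-point figure is used up once about 4 of the 100 leave the base. By the exact method it is already passed at n = 100. There the largest distance from estimate to limit, over all rates, is 10.29 points, and a base of 106 would be needed to bring it to 10 or below (9.98).

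**Step 3: away from 50%.** The Wald half-width stays within 10 points when p(1 − p) ≤ 0.01n/1.96². At n = 80 the bound is 0.8/3.84 = 0.208, so the figure still holds for rates up to about 30% or from about 70%. At n = 60 the bound is 0.156, so it holds up to about 19% or from about 81%.

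**Scope.** These binomial figures apply to tick-box measures such as Question 3. Question 2 asks for a numerical percentage. The precision of its mean also depends on the number contributing, but through a between-provider spread that the protocol does not give.

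**The case against.** The strongest reply is that the base may well be 100. The quota counts completed questionnaires, not entrants. Section 5 says every eligible respondent answers the same Appendix B questions, and no skip pattern is shown. Section 3.4 aims at likely prescribers and calls the replacement draw a sample of prescribers. The screening questions are not visible, since Appendix B starts at Screen 3. The answered-only denominator is stated for the combined behaviours and not for each activity. An unticked box can be read as not done, and a provider without patients can enter 0% in Question 2. Both would then stay in the base.

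Much of this stands. A reader might infer that the outcome base does fall below 100 and that the promised precision is not delivered. The documents do not support that: they give no share of providers without treated patients and no rule that removes them. Nor is Table 1 miscalculated.

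The reply still does not secure the statement. With no 'none' option, a blank Question 3 cannot be told apart from an unanswered one, so the answered-only rule has no clear base. If blanks are kept as 'not done', n stays at 100 but the rate describes something else. As an illustration, suppose 20 of 100 have no treated patients and half of the other 80 perform an activity: the reported rate is 40/100 = 40%, not 50%. The precision is then kept at the expense of what is measured.

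It is also fair that the shortfall is moderate. A 20% loss costs about 1.2 points at a rate of 50% by either method, no success threshold is set, and pooled over 800 the Wald half-width is only 1.96 × √(0.25/800) = 3.5 points. Section 3.3, however, sets and justifies the sample by country.

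**Conclusion.** The concern holds in conditional form: the stated per-country precision for outcome measures is not assured. It depends on nearly all 100 completed questionnaires contributing to Questions 2 and 3, and eligibility, the Question 3 wording and the denominator rule do not ensure that. Under the exact intervals of Section 6, the 10-point ceiling is slightly exceeded near mid-range rates even with a full base (10.2 points at 50%, 10.3 at most). That small excess applies to process measures too. With smaller outcome bases the figure at 50% would be about 11.4 points at 80 and 14.5 at 50. Those bases are assumptions, not estimates from the protocol, and at rates well away from 50% a base of 80 would still meet the stated limit.

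**What to change.** In Section 3.3, state precision separately by type of measure, using the exact intervals of Section 6:

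- **Process measures:** up to about 10.2–10.3 points at n = 100.
- **Outcome measures:** dependent on the number contributing; for example, about 11.4 points at an assumed base of 80 and 14.5 at an assumed base of 50, for a rate near 50%.

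Let this conditional statement replace the claim that the precision holds at any level of the measure. Define the outcome base as respondents with treated patients who answered the activity questions, and report that base with each outcome percentage. If the screening module does not already identify providers without treated patients, the questionnaire must be able to do so, or the base cannot be counted. Reconcile the two wordings of Question 3 at the same time, since they imply different bases.

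The cost is wording, a few table entries and possibly one response option. No extra respondents are needed. The stated precision becomes slightly less favourable.

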1. BACKGROUND

The MEB, as the Reference Member State (RMS) for SEROQUEL and SEROQUEL XR, requested AstraZeneca to update the education materials in scope of the EU Risk Management Plan (RMP) and Summary of Product Characteristics (SmPC) changes with respect to hyperglycaemia and metabolic monitoring. The content and the messages for these educational materials have been agreed and distribution in the individual member states is ongoing.

AstraZeneca was also requested to provide a plan for assessing the effectiveness of these educational materials. During discussion with the MEB, it was communicated that there are 2 components to the assessment of effectiveness: process indicators (receipt and understanding of materials) and outcome indicators (changes in behaviour and effect on patients). To realize these 2 indicators, AstraZeneca is proposing 2 components for the evaluation of the effectiveness of the metabolic education: an objective, easy to understand and complete healthcare provider survey and the use of an Electronic Medical Records approach, as a potential means to assess the monitoring of patients.

This protocol describes the evaluation of the effectiveness of the distribution of metabolic educational materials sent to healthcare providers in the EU. It will be conducted via an evaluation survey that uses a questionnaire to assess the receipt of the educational material, whether the material was read, and to assess healthcare provider behaviour regarding the conduct of monitoring of metabolic parameters for patients treated with SEROQUEL and SEROQUEL XR. The survey will be conducted among healthcare providers who were targeted to receive the educational materials following local guidance and directives.

A companion proposal describes the evaluation of electronic medical record (EMR) data including details on objectives, the source of data, and the target healthcare provider-base for the database assessment.

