3.1 Study Design

This survey will be completed by a sample of healthcare providers who were targeted to receive the metabolic educational materials and either currently prescribe or have the potential to prescribe SEROQUEL or SEROQUEL XR. A sample of healthcare providers who were targeted for the educational materials will be approached to participate in the survey.

The survey will be administered using the following modality:

• Self-administered and Internet-based questionnaire accessed through a secure website instructing the participant to enter a unique code provided in the invitation.

The survey will begin with screening questions to confirm respondent eligibility to participate in the survey. Completion of the entire survey is expected to take less than 10 minutes.

The survey included in Appendix B is written to reflect the wording and screen-by-screen presentation of questions for an Internet-based survey administration.

All respondents who complete the survey and who provide their contact information will be mailed a fee consistent with approved market value for the physician's time for completing the survey.

The questions related to having received the educational materials and having read the information (measures of process) are closed-ended questions (answered affirmatively as yes/no/unsure response options). Questions related to physician behavior regarding monitoring of patients (measures of outcome) are percentage estimates provided by the physician.

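### Section 3.3 reads the 95% limits of a one-time reported monitoring level as bounds on effectiveness, although the outcome indicator is change in behaviour

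*Protocol*

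**What the plan says.** - **Purpose (Section 1).** The survey's aim is given as follows: "This protocol describes the evaluation of the effectiveness of the distribution of metabolic educational materials sent to healthcare providers in the EU". The same section separates process indicators (receipt and understanding) from "outcome indicators (changes in behaviour and effect on patients").
- **Who is asked (Section 3.1).** The respondents are "a sample of healthcare providers who were targeted to receive the metabolic educational materials". No untargeted group is sampled.
- **What is asked (Section 3.1.1 and Appendix B).** Section 3.1 calls the monitoring questions measures of outcome. Both are in the present tense. Question 2 asks "What proportions of your patients are being monitored by you, someone else in your practice or are referred to other healthcare providers", and Question 3 asks "which of the following activities do you perform? Please check all that apply". No item asks about practice before the materials arrived.
- **How the result is to be read (Section 3.3).** The plan is "A sample size of 100 completed questionnaires from healthcare providers in each of eight selected countries", with no target rate for process or outcome measures. Of the 95% intervals it says that "for any survey-estimated level of effectiveness of risk minimization, the true population level of effectiveness is at least as high as the lower limit", and that it may be as high as the upper limit. The Table 1 title names performance of metabolic monitoring as the outcome measure covered.
- **What is reported (Section 6).** The list of outputs includes "Percent of respondents demonstrating success of composite risk minimization activities and 95% confidence interval". No before/after contrast, and none by receipt or reading, is named.

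**The concern.** A confidence interval for the percentage of providers who report an activity bounds the prevalence of that report. Section 3.3 says that it bounds something else, the population level of effectiveness of risk minimisation. The two would coincide only if nobody had monitored before the materials were sent. The protocol gives reason to doubt that: the key messages in Section 2 refer to antipsychotic guidelines already in use and describe the lipid and metabolic-risk information as existing.

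The survey answers a regulator's request to assess whether the materials work. If the monitoring percentages reach the report under the labels *effectiveness* and *success*, with a lower limit presented as a floor, providers who monitored all along count in full towards the effect of the materials. Nothing else in the protocol, such as a reference rate, a baseline or a comparison group, would let a reader separate the two.

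**Working it through.** **Inputs.** From Section 3.3: n = 100 per country, two-sided 95% intervals, and the 17 rows of Table 1. The level of monitoring before distribution is not given, so assumed values are used and marked as such.

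**Step 1: reproduce Table 1.** The normal-approximation interval for one proportion is p ± 1.96 × √(p(1 − p)/n), cut off at 0.
- For p = 0.76: √(0.76 × 0.24/100) = 0.0427, and 1.96 × 0.0427 = 0.0837. The limits are 67.6% and 84.4%, as in Table 1.
- For p = 0.51: the half-width is 9.8 points and the limits are 41.2% and 60.8%, as in Table 1.
- All 17 rows agree. The arithmetic of the table is sound for what it computes.
- The exact binomial interval named in Section 6 gives 66.4% to 84.0% at 76%. The choice of interval does not affect this point.

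**Step 2: see what the formula contains.** It has two inputs, the observed p and n. There is no term for an earlier level or a comparator. At an observed 76%:

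| Level before distribution (assumed) | Level after | Change | Interval that Section 3.3 reads as effectiveness |
|---|---|---|---|
| 40% | 76% | +36 points | 67.6% to 84.4% |
| 76% | 76% | 0 points | 67.6% to 84.4% |
| 90% | 76% | −14 points | 67.6% to 84.4% |

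An improvement, no change and a decline all give the same stated bounds.

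**Step 3: compare with an interval for change.** Suppose, as an assumption only, that an independent sample of 100 had been surveyed before distribution and both samples showed 76%. The estimated change is 0, with half-width 1.96 × √(2 × 0.76 × 0.24/100) = 11.8 points, so the interval is −11.8 to +11.8 points. The single-survey interval of 67.6% to 84.4% differs from this in location, in width (half-width 8.4 points) and in the quantity it describes.

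**Scope of the arithmetic.** The single-proportion formula fits the tick-box activities in Question 3. Question 2 asks each physician for a percentage estimate, so these figures do not carry over to it. The interpretive point does, because Question 2 also records only a current level.

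**The case against.** The strongest reply is that this is loose wording in a sample-size section. Read whole, the sentence is a lay explanation of a two-sided interval, and the Table 1 title shows that the rate is performance of monitoring. The analysis is descriptive. The reference to changes in behaviour reports the regulator's view of the whole programme, which also has a companion evaluation of electronic medical records. The survey's own stated scope is to assess behaviour.

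Much of this stands, and it rules out several stronger readings that a reader might infer:

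- *The protocol would declare useless materials effective.* It would not. Section 3.3 sets no target rate, and Section 6 plans frequencies, percentages and intervals. There is no verdict and no ranking of countries.
- *The lower limit almost always exceeds zero even with no effect.* This is true but uninformative. An exact lower limit is above zero as soon as one respondent ticks the box, and the protocol uses no zero threshold.
- *The programme as a whole cannot show change.* This cannot be judged, because the design of the medical-records evaluation is not shown.
- *A contrast of readers with non-readers is missing.* Question 4 would allow one, and an analysis plan not shown might contain it, so its absence is no fault here.
- *Receipt and reading are affected too.* They are not. A one-time level is a suitable quantity for a process measure.

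None of this alters what Section 3.3 says the limits bound for the monitoring measure. If the survey is purely descriptive, the sentence that interprets its intervals should be descriptive as well.

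**Conclusion.** The point holds as a fault of interpretation, not of arithmetic. For the monitoring questions, Section 3.3, the Table 1 title and Section 6 attach *effectiveness* and *success* to a rate that measures current reported practice, and Section 3.3 offers its 95% limits as bounds on true effectiveness. This design cannot support that reading. The mislabelled amount is whatever monitoring existed before distribution. The documents do not give that figure, and it could be anything from none to all of the observed level. At an observed 76%, for instance, the whole of 67.6% to 84.4% could be background practice.

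The conclusion rests on the questionnaire and analysis as written in the protocol and needs no assumption about the true background level. It should be corrected because the results go to a regulator who asked about effectiveness. It changes no planned sample size or interval calculation.

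**What to change.** **Wording (the essential part).** For the Question 2 and 3 results in Section 3.3, the Table 1 title and Section 6, replace *effectiveness* and *success* with *reported monitoring after distribution*. Add a sentence stating that the 95% interval bounds that level only, and that no conclusion about change or effectiveness will be drawn from it. The process measures can stay as levels of receipt and reading. This costs a few lines of text.

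**Optional, if the survey is to speak to behaviour change.** Before translation, add one closed item for each of the six activities listed in Question 3, asking about change since receipt of the 2012 materials: already did / started or increased / reduced or stopped / not sure. Ask it for every listed activity, not only those ticked, so that reductions can be seen. Report the answers descriptively with the exact 95% intervals already planned in Section 6.

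This needs no extra respondents, but the items should go through the planned face-validity and pilot steps, including a check that completion still takes under 10 minutes. The report should acknowledge recall and social-desirability bias, and that such an item cannot separate the materials from other influences on practice.
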